### **6.5.2 Rationale for study design and control groups**

This study is designed to demonstrate the efficacy by slowing the progression of kidney volume and concomitantly evaluate the effect on worsening renal function, patient reported outcome (PRO) and liver volume in patients with ADPKD. Due to the high variability of eGFR, the primary endpoint of Stage 1 is TKV growth rate while the primary endpoint in Stage 2 is the slope

of eGFR. Safety, tolerability, PK, and PD effects of venglustat are supported by Phase 1 and Phase 2 studies and animal toxicology data in rodents up to 26 weeks and dogs up to 39 weeks. In vitro and in vivo genotoxicity studies have been conducted and are negative. Carcinogenicity studies have not yet been conducted.

A prognostic enrichment approach is used to select patients for primary analysis population who will be at risk for rapid progression of disease based on those aged between 18 to 50 years, CKD Stages 2-3A, and Mayo Imaging Classification of ADPKD Class 1C-E. This enrichment allows the detection of treatment benefit on both TKV and GFR in the same population thus circumventing the need for performing separate trials in "early" and "late" ADPKD patients.

Patients with eGFR  $<45$  mL/min/1.73 m^2 aged 18 to 55 years old recruited in Stage 2 of the study will be not included in primary analysis population but the data from these patients will be analyzed separately.

Patients with CKD Stage 3b (eGFR 30 - 45 mL/min/1.73 m^2) aged 18 to 55 years old will be recruited in Stage 2 of the study to permit gathering information on venglustat in this severely affected patient population. However, this patient population will not be included in the Stage 2 primary analysis but will be analyzed separately. The rationale for including these patients in the study is to obtain further information on venglustat exposure, safety and efficacy in patients with lower renal function.

Based on the mode of action of venglustat the benefit of disease modification is expected to decrease whereas the exposures of venglustat increase with declining renal function. For this reason, CKD Stage 4 patients (eGFR  $<30$  mL/min/1.73 m^2) will not be included into the study.

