### **11.3.2 Safety population**

The Stage 1 Safety population will be defined as all patients who are randomized in Stage 1 and received at least one dose or part of a dose of the double-blind IMP, analyzed according to the treatment actually received (venglustat 15 mg, venglustat 8 mg, or placebo)

The combined Stage 1 and Stage 2 Safety population will be defined as all patients with an eGFR between 45 and 89.9 mL/min/1.73 m^2 at screening who are randomized in Stage 1 or Stage 2 and received at least one dose or part of a dose of the double-blind IMP, analyzed according to the treatment actually received (venglustat 15 mg, venglustat 8 mg, or placebo). Patients from Stage 2 with an eGFR between 30 and 44.9 mL/min/1.73 m^2 at screening will not be included in the primary safety analysis population but the data from these patients will be analyzed separately.

A secondary safety analysis population will include patients who are randomized in Stage 2 with an eGFR between 30 and 44.9 mL/min/1.73 m^2 at screening and received at least one dose or part of a dose of the double-blind IMP.

In addition:

- Nonrandomized but treated patients will not be part of the safety population, but their safety data will be presented separately.
- Randomized patients for whom it is unclear whether they took the study medication will be included in the safety population as randomized.
- For patients receiving more than 1 study treatment during the trial, the treatment group allocation for as-treated analysis will be the one to which the patient was treated with the longest duration.

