SAP Version	Approval Date	Changes	Rationale
		The two-step analysis is not applicable anymore and replaced by a single analysis of all data available on combined Stage 1 & Stage 2 analysis (see Section 1.1 and Section 4.9.3)	Following decision to discontinue EFC15392 and LTS15823 studies based on EFC15392 futility analysis
		Efficacy analyses on Stage 1 ITT population and combined Stage 1 and Stage2 population will be conducted on all data available up to database lock (see Section 4.1, Section 4.3.1). No multiple imputation will be done, only analysis on observed data will be performed (see Section 1.2.1, Section 4.3.1.1, Section 4.3.1.2, and Section 4.3.2.2).	
		As no post-baseline MRI data will be available in Stage 2 at the time of the study discontinuation, the analysis of TKV and TLV in Combined Stage 1 and Stage 2 will not be done (see Section 1.2.1, Section 4.4.2.2 & Section 4.5.2).	
		Secondary analysis of eGFR on all randomized participants will be replaced by descriptive summary across visit on the secondary Stage2 ITT population (see Section 3 and Section 4.3.2.4)	
		For all tertiary endpoints, due to the high number of missing data at month18 and month24, MMRM will be replaced by only descriptive summary by visits (see Section 4.5.2, Section 4.8.2, Section 4.8.3 and Section 4.8.4). For the secondary endpoints (BPI-Item3 & BFI Item3), in case the MMRM does not converge due to high number of missing data, then only descriptive summary by visits will be provided (see Section 4.4.1.2 and Section 4.4.2.2)	
		As no GM3 sample tested at the time of the study discontinuation, the analysis of GM3 will not be done (see Section 4.8.2)	
		Safety populations and all safety analyses on Stage 1 populations are removed. All safety analyses will be performed on the extended combined Stage 1 and Stage 2 safety population, including all participants with an eGFR between 30 and 89.9 mL/min/1.73 m ² at screening (see Section 3 and Section 4.7).	
		mGFR analysis has been removed as no data available (see Section 4.5.1).	

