2 SAMPLE SIZE DETERMINATION

In Stage 1, approximately 240 participants will be randomized (with randomization ratio 1:1:1) to placebo (n=80) or venglustat 8 mg (n=80) or venglustat 15 mg (n=80mg).

In Stage 2, approximately 320 participants with an eGFR between 45 and 89.9 mL/min/1.73 m² at screening will be randomized (with randomization ratio 1:1) to placebo (n=160) or venglustat (n=160).

In addition, 80 participants with an eGFR between 30 and 44.9 mL/min/1.73 m² at screening will be randomized (with randomization ratio 1:1) to placebo (n=40) or venglustat (n=40). The participants from Stage 2 with an eGFR between 30 and 44.9 mL/min/1.73 m² will not be included in the primary efficacy and safety analyses populations but the data from these participants will be analyzed separately.

This sample size will provide approximately 89% power to detect a 50% reduction in annualized rate of change in TKV at end of Stage 1 and approximately 87% power to detect a 30% reduction in annualized rate of change in eGFR between venglustat and placebo at the end of Stage 2. Overall, the total sample size will provide approximately 87% power to detect an effect on both TKV and eGFR.

Sample size and power calculations were based on simulations, assuming different scenarios regarding the dose-response relationship (Section 5.6.1). SAS program is provided in (Section 5.5). The following model parameters were estimated based on available datasets from a similar participant population (participants aged 18 to 50 years with Mayo class 1C-1E and baseline eGFR from 45 to 90 mL/min/1.73 m²) in 2 historical studies (Consortium for Radiologic Imaging Studies of Polycystic Kidney Disease (CRISP) and the Polycystic Kidney Disease Treatment Network ([HALT-PKD]):

- A slope of log10(TKV) of 0.02591, 0.02832 and 0.03141 in participants from Mayo class 1C, 1D and 1E respectively (corresponding to 6.1%, 6.7% and 7.5% increase per year in TKV), resulting in average slope of 0.02764 (6.6%/year) assuming 50% of 1C, 33% of 1D and 17% of 1E.
- Standard deviation for the residual error of TKV (on the log10 scale) of 0.02566 and standard deviation for the random effect of slope of 0.01477.
- A slope of eGFR of -3.16, -3.88 and -4.69 mL/min/1.73 m² per year in participants from Mayo class 1C, 1D and 1E respectively, resulting in average slope of -3.66 mL/min/1.73 m² per year assuming 50% of 1C, 33% of 1D and 17% of 1E.

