3 ANALYSIS POPULATIONS

The following populations for analyses are defined:

Table 4 - Populations for analyses

Population	Description
Screened	All participants who signed the Informed Consent Form (ICF).
Randomized	All participants from screened population who have been allocated to a randomized intervention by Interactive Response Technology (IRT) regardless of whether the intervention was received or not.
Exposed	All screened participants who took at least 1 dose of study intervention.
Population without trial impact (disruption) due to COVID-19	All randomized participants without any critical or major deviation related to COVID19 and who did not permanently discontinue treatment due to COVID19 and who did not permanently discontinue study due to COVID19
Stage 1 Intent-to-treat (ITT)	All participants randomized in Stage 1.
	Participants will be analyzed according to the intervention allocated by randomization (venglustat 15 mg, venglustat 8 mg or placebo).
Stage 1 Pharmacokinetic (PK)	All participants randomized in Stage 1 who took at least 1 dose of study intervention and who have at least one post-baseline PK assessment. Participants will be analyzed according to the intervention they actually received.
Stage 1 Pharmacodynamic (PD)	All participants randomized in Stage 1 who took at least 1 dose of study intervention and who have at least one post-baseline PD assessment. Participants will be analyzed according to the intervention they actually received.
Combined Stage 1 and Stage 2 ITT	All participants with an eGFR between 45 and 89.9 mL/min/1.73 m ² at screening who are randomized in Stage 1 or Stage 2.
	Participants will be analyzed according to the intervention allocated by randomization (venglustat 15 mg, venglustat 8 mg or placebo).
Secondary Stage 2 ITT	All participants with an eGFR between 30 and 44.9 mL/min/1.73 m ² at screening who are randomized in Stage 2. Participants will be analyzed according to the intervention allocated by randomization (venglustat 15 mg or placebo).
Extended Combined Stage 1 and Stage 2 Safety	All participants with an eGFR between 30 and 89.9 mL/min/1.73 m ² at screening who are randomized in Stage 1 or Stage 2 and who took at least 1 dose of study intervention. Participants will be analyzed according to the intervention they actually received.

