4 STATISTICAL ANALYSES

4.1 GENERAL CONSIDERATIONS

In general, continuous data will be summarized using the number of observations available, mean, standard deviation (SD), median, [Q1, Q3] minimum, and maximum. Categorical and ordinal data will be summarized using the count and percentage of participants.

The baseline value is defined as the last available value before or equal to the first dose of double-blind investigational medicinal product (IMP). For participants randomized but not exposed, the baseline value is defined as the last available value before or equal to the date and time of randomization.

Baseline eGFR is defined for each participant as the average of eGFR values assessed prior or equal to first IMP, or randomization for participants randomized and not exposed.

Baseline of patient daily diaries scores is defined for each participant as the average of the assessments during the 7 days prior the 1st IMP or prior randomization for participants randomized and not exposed.

Baseline of urine osmolality is defined as the average of the 3 separate assessments within the 3 days prior or equal to the baseline visit (Visit 3).

Primary efficacy analyses will be conducted on Stage 1 ITT population and on combined Stage 1 and Stage 2 ITT populations (see Section 3), including all data available at the time of database lock from baseline to Month 24:

• Participants from Stage 2 with an eGFR between 30 and 44.9 mL/min/1.73 m² at screening will not be included in the primary efficacy analysis. A supplemental descriptive efficacy analysis on these participants will be performed separately (see Section 3 and Section 4.3.2.4).

Safety analyses will be conducted in the extended combined Stage 1 and Stage 2 population (see Section 3) including all data available from baseline to the end of the 24-month double-blind treatment period. Unless otherwise specified, analyses will be performed by intervention group (and overall for baseline and demographics characteristics).

Observation period

The observation period will be divided into 4 segments:

- The **pre-treatment period** is defined as the period up to first IMP administration.
- The **treatment-emergent** (TE) **period** is defined as the period from the first IMP administration up to the last IMP administration in EFC15392 study +30 days or up to the first visit in LTS15823 study, whichever comes earlier. The treatment-emergent period includes the following 2 periods:

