4.7 SAFETY ANALYSES

All safety analyses will be performed on the Extended combined Stage 1 and Stage 2 safety population as defined in Section 3, unless otherwise specified, using the following common rules:

- The analysis of the safety variables will be essentially descriptive, and no testing is planned.
- Safety data in participants who do not belong to the safety population (eg, exposed but not randomized will be provided separately if any.

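### SAP version 2 pools the Stage 2 eGFR 30–44.9 cohort into its only safety population, gives no cohort-specific reason, and leaves the cohort without a prespecified safety summary

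*SAP*

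**What the plan says.** **Protocol.** Section 11.3.2 limits the combined safety population to screening eGFR 45–89.9. It says that Stage 2 patients at 30–44.9 "will not be included in the primary safety analysis population but the data from these patients will be analyzed separately". It then gives them their own set: "A secondary safety analysis population will include patients who are randomized in Stage 2 with an eGFR between 30 and 44.9", with at least one dose or part of a dose taken. Section 6.5.2 explains why they were recruited: "to obtain further information on venglustat exposure, safety and efficacy in patients with lower renal function".

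**SAP version 2, Section 2.** The cohort "will not be included in the primary efficacy and safety analyses populations but the data from these participants will be analyzed separately".

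**SAP version 2, Sections 3, 4.1 and 4.7.** Table 4 lists one safety population, the extended combined set: "All participants with an eGFR between 30 and 89.9 mL/min/1.73" m² who were randomized in either stage and dosed. Section 4.1 assigns safety to that set, and Section 4.7 repeats it ("All safety analyses will be performed on the Extended combined Stage 1 and Stage 2 safety population as defined in Section 3"), subject to an unless-otherwise-specified clause. For the 30–44.9 cohort, Section 4.1 keeps only this apart: "A supplemental descriptive efficacy analysis on these participants will be performed separately". Section 4.3.2.4 shows that to be a summary of eGFR by visit.

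**SAP Table 1.** The version 2 log declares the change: "All safety analyses will be performed on the extended combined Stage 1 and Stage 2 safety population". The entry states the 30–89.9 range and sits in the block of changes attributed to the decision to discontinue the study.

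**The concern.** Section 2 and Sections 3, 4.1 and 4.7 of the same SAP version give different rules for the same patients, and both cannot be followed. If the later sections govern, as seems intended, the protocol's separate safety set disappears and nothing replaces it.

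What is at stake is a stated purpose of the cohort. Protocol 6.5.2 says that exposure rises as renal function falls, and that safety in these patients was one of the things to be learned. The cohort also has a higher age limit (55 rather than 50, inclusion criterion I 01), which may matter for lens findings, an adverse event of special interest. If only pooled tables are produced, a difference between 15 mg and placebo that arose mainly in this cohort would be hard to see, and nobody reading the planned outputs could say what happened in the cohort.

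**Working it through.** **1. Does any safety output describe the cohort?** I looked in SAP 4.7.1 to 4.7.3.5 for anything that uses the unless-otherwise-specified clause.

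| Output | Split by screening eGFR? |
|---|---|
| Exposure and compliance (4.7.1) | No; extra cut by COVID-19 impact only |
| TEAE, SAE, AESI, deaths (4.7.2) | No; extra cut by COVID-19 impact only |
| Laboratory, vital signs, ECG, PCSA (4.7.3.1) | No; PCSA baseline status is normal/missing versus abnormal |
| Physical and neurological examination (4.7.3.2, 4.7.3.3) | No |
| Ophthalmology (4.7.3.4) | No |
| BDI-II (4.7.3.5) | No |

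None does. The Stage 2 PK population in Table 4 is also restricted to 45–89.9, so the cohort's exposure is not summarised there either.

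**2. Planned numbers (SAP Section 2, Protocol 11.1).** Stage 1: 80 per arm in three arms. Stage 2 at 45–89.9: 160 per arm. Stage 2 at 30–44.9: 40 per arm.

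Check against the plan's own totals: 2 × (160 + 40) = 400 in Stage 2, as in the Clinical Trial Summary; 240 + 400 = 640 overall, as in Protocol 9.4.14.1. Both reproduce.

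Stage 2 used 15 mg (SAP 1.1), so the cohort enters only the 15 mg and placebo groups. Each has 80 + 160 + 40 = 280 patients at plan. Cohort share = 40/280 = 14.3%.

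**3. Dilution.** If the two arms differ only within the cohort, the pooled risk difference is the cohort's difference × 40/280, a factor of 280/40 = 7.0.

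Two illustrations follow. All event rates are assumed, with the same background rate inside and outside the cohort. Power is nominal, two-sided 0.05, and is shown only as a gauge of visibility, because SAP 4.7 plans no safety testing.

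| Background | Cohort on 15 mg | Separate table | Pooled table | Power, separate / pooled |
|---|---|---|---|---|
| 10% | 20% | +10 points, ratio 2.0 | 10% + 10/7 = 11.4%: +1.4 points, ratio 1.14 | 0.24 / 0.08 |
| 5% | 25% | +20 points, ratio 5.0 | 5% + 20/7 = 7.9%: +2.9 points, ratio 1.57 | 0.72 / 0.28 |

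**4. Sensitivity to enrolment.** The documents do not give the numbers enrolled at the stop. Take Stage 1 as full.

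- Stage 2 at a fraction f of plan with its 4:1 mix kept: factor = (80 + 200f)/(40f). This gives 7.7 at 75%, 9.0 at 50% and 13.0 at 25%.
- Cohort full at 40 per arm, main Stage 2 group at 80 or 120 per arm: (80 + 80 + 40)/40 = 5.0 or (80 + 120 + 40)/40 = 6.0.

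**5. What a separate table could show.** In the first illustration, 8/40 versus 4/40 is a difference of 10 points with standard error √(0.2 × 0.8/40 + 0.1 × 0.9/40) = 7.9 points, so an approximate 95% interval of −5.5 to +25.5 points.

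**The case against.** Four points on the other side deserve weight.

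**The change is declared.** A reader might infer that the SAP silently departs from Protocol 11.3.2. It does not: Table 1 logs the new population and its eGFR range. What remains is that the only rationale is study discontinuation, which does not explain why this cohort should be merged or its own summary dropped.

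**The internal conflict is probably a leftover.** Table 1, Table 4, 4.1 and 4.7 agree; only the sample-size text in Section 2, which mirrors Protocol 11.1, was not updated. A programmer would most likely use the extended set. That lowers the risk of confusion but leaves the missing cohort summary untouched.

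**The data survive.** A reader might conclude that the trial can no longer answer the safety question. That goes too far. Treatment was randomized and screening eGFR is derived for every participant (SAP 5.4), so the subset can be tabulated at any time. What is lost is prespecification. The early stop may limit the answer more than the table layout: Table 1 says that Stage 2 had no post-baseline MRI, a scan due at Month 18.

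**Nothing shows that harm is confined to this cohort.** The 1.33-fold AUC (90% CI 1.09 to 1.62) in Protocol 6.5.1 is a single-dose result for moderate impairment. The same section uses GFR 30–60 as the moderate range, which takes in main-population patients at 45–59.9. The protocol also predicts mean steady-state exposure in that range within exposures already observed. The dilution figures therefore show what pooling would do to such a signal, not that one is expected.

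Small cells are a fair caution, as the wide interval above shows. They argue for a descriptive summary, not for none.

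**Conclusion.** The point stands in limited form. SAP version 2 removes a protocol-defined safety population, declares the removal without a cohort-specific reason, and leaves Section 2 saying the opposite. As written, no prespecified safety output describes the eGFR 30–44.9 cohort.

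The size is about seven-fold, on three conditions: planned enrolment, an absolute risk difference, and an effect confined to the cohort. Under the enrolment scenarios above the factor runs from 5 to 13. A reader might take seven-fold to apply to relative risk as well; it does not. The ratio falls by less (2.0 to 1.14 in the first illustration) and depends on the background rate. No efficacy conclusion or error rate is affected.

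**What to change.** 1. In SAP Table 4, restore the secondary safety population: Stage 2, screening eGFR 30–44.9, at least one dose.
2. In SAP 4.7, add descriptive by-arm summaries for it beside the pooled tables. At a minimum these are the TEAE overview, SAE, AESI including lens findings, and AE leading to treatment discontinuation. The protocol requires separate analysis but no particular table list, so repeating every safety table in two eGFR strata is not necessary.
3. Make Section 2 agree with Sections 3, 4.1 and 4.7, and state in Table 1 why the cohort also enters the pooled set.

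The cost is a wording change and a re-run of existing programs on a subset defined by a variable already derived. No new data are needed. The downside is small cell counts, so the summaries should be labelled descriptive, with the actual number per arm shown.

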4.7.1 Extent of exposure

The extent of IMP exposure will be assessed by the duration of IMP exposure and compliance and summarized on the Extended combined Stage 1 and Stage 2 safety population.

In addition, summaries will be provided in the population with trial impact (disruption) due to Covid-19.

Duration of IMP exposure

Duration of IMP exposure is defined as last IMP administration date – first IMP administration date + 1 day, regardless of unplanned intermittent discontinuations. If the date of the last dose of IMP is missing, the duration of IMP will be left as missing.

Duration of IMP exposure will be summarized quantitatively and categorically:

- ≥1 day
- >1 Month
- >3 months
- ≥ 6 months
- ≥ 12 months
- \geq 15 months
- >18 months
- \geq 21 months
- >24 months

Additionally, the cumulative duration of treatment exposure (expressed in participant-years) will be provided.

Treatment compliance

A given administration will be considered noncompliant if the participant did not receive the number of days of IMP as required by the protocol. No imputation will be made for participants with missing or incomplete data.

Percentage of treatment compliance for a participant will be defined as the number of days of IMP administered divided by the total number of days that the participant was planned to take from the first administration of IMP up to the actual last administration of IMP.

Treatment compliance will be summarized quantitatively and categorically: <80%, $\ge80\%$.

Cases of overdose are reported in the adverse event (AE) e-CRF pages as Adverse Event of Special Interest (AESI) if symptomatic or AE if asymptomatic. The reported cases of overdose will be described in the AE analysis (see Section 4.7.2).

